### 3.5 Safety Endpoints

---

Safety evaluations include AE monitoring, physical examinations, vital sign measurements, electrocardiogram (ECG) variables (as needed), and clinical laboratory testing (hematology, chemistry, and urinalysis) as measures of safety and tolerability. An internal DMC will monitor safety at regular intervals (Section 6.3).

### 3.6 Pharmacokinetic Endpoints

---

Serum ravagalimab concentrations will be obtained at the visits indicated in [Appendix D](#) and will be summarized at each sampling time point using descriptive statistics. A nonlinear mixed-effects modeling approach may be used to estimate the population central value and the empirical Bayesian estimates of the individual values for ravagalimab apparent clearance (CL/F) and volume of distribution at steady-state (Vss/F). Ravagalimab anti-drug antibody (ADA) development will also be determined at specific visits during the study ([Appendix D](#)) and will be summarized using descriptive statistics. Additional parameters and relationships (e.g., exposure-receptor occupancy, exposure-efficacy, or exposure-safety) may be evaluated if useful for the interpretation of study results.

### 3.7 Biomarker Endpoints

---

Biospecimens (blood and tissue biopsy) will be collected at specified time points ([Appendix D](#)) throughout the study to evaluate known and/or novel disease-related or drug-related biomarkers. Types of biomarkers may include nucleic acids, proteins, lipids, and/or metabolites. Biopsies for biomarker analysis will be done when performing endoscopies. Up to 4 biopsies will be taken from the site of general inflammation at each visit with an endoscopy for biomarker research as outlined in [Appendix D](#): 1 biopsy for histologic assessment by central review, 1 biopsy for gene expression analysis (including CD40 signature), and 2 biopsies for tissue RO (where applicable). Biopsies for tissue RO will only be collected at sites located in the United States. Additional biopsies may be collected at the Investigator's discretion to confirm disease diagnosis, and/or to rule out dysplasia, colon cancer and infection.

Blood samples will be used to evaluate ravaglimab RO and change in T cells, NK cells, B cells, and plasmablast cell numbers.

Blood samples may be used for exploratory research to assess and generate prognostic, predictive, pharmacodynamic, or surrogate biomarker signatures. Mandatory intestinal biopsy tissue samples may also be used for exploratory research to assess and generate prognostic, predictive, pharmacodynamic, or surrogate biomarker signatures. These assessments may be explored in the context of UC or related conditions and/or ravaglimab or drugs of similar classes.

The results from these analyses are exploratory in nature and may not be included with the clinical study report. Biomarker samples will be collected and analyzed from all subjects, unless precluded by local regulations or restrictions.

## 4 INVESTIGATIONAL PLAN

### 4.1 Overall Study Design and Plan

---

Study M15-722 is a Phase 2a, multicenter, single arm, open-label (OL) study to investigate the efficacy and safety of ravaglimab in subjects with moderate to severe UC who failed prior therapy. The study contains a 35-day screening period, 2 treatment periods, and an 84-day follow up period from the last dose of study drug. The induction period is an open-label 12-week treatment period to evaluate the efficacy, safety, tolerability, PK and RO of ravaglimab for inducing endoscopic improvement at Week 8. Subjects who achieve clinical response per Partial Adapted Mayo score at Week 12 may continue into the maintenance period. The maintenance period is an OL 92-week treatment period to assess efficacy and safety for maintenance of response with ravaglimab.

Prior to protocol version 4.0 the study had a double-blind (DB) placebo-controlled induction period. Ongoing subjects enrolled prior to version 4.0 continued their treatment as randomized during the induction period and, in case of clinical response at Week 12, their OL treatment during the maintenance period.

#### **Induction Period**

Up to approximately 40 subjects will be enrolled in the induction period to receive the following treatment:

- Ravaglimab 600 mg intravenous (IV) Week 0; ravaglimab 300 mg subcutaneous (SC) Weeks 2, 4, 6, 8, and 10.

Once the 30th subject completes Week 8 assessments an interim analysis will occur. This interim analysis will inform the planning of future Phase 2b and 3 studies. Enrollment into the induction period may continue until approximately 40 subjects have enrolled, or enrollment may be terminated if the study objectives are determined to have been met.

An endoscopy is required at Screening, and evaluation of endoscopic improvement will occur at Week 8. In order to explore the time-course of ravaglimab efficacy, subjects will continue through Week 12 and

will be assessed for clinical response per Partial Adapted Mayo score at Week 12. Subjects who complete the induction period and achieve clinical response per Partial Adapted Mayo score at Week 12 will be given the opportunity to continue into the maintenance period. Subjects not achieving clinical response per Partial Adapted Mayo score at Week 12 will be discontinued and have a follow-up visit (or call if a visit is not possible) 84 days from the last dose of study drug to obtain information on any new or ongoing AEs.

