### Interim Analysis

An interim efficacy analysis will be performed after approximately 30 subjects complete Week 8 assessments. This interim analysis will inform the planning of future Phase 2b and 3 studies. Enrollment into the induction period will continue until approximately 40 subjects have been enrolled.

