### Sample Size Estimation and Decision Probability

The planned sample size is up to approximately 40 subjects.

Meta-analysis for historical placebo data from tofacitinib (OCTAVE1/2), upadacitinib (Phase 2b; data on file) and ustekinumab (UNIFI) studies gives [REDACTED] endoscopic improvement rate at Week 8. The matched prior distribution for placebo is [REDACTED]. The prior for ravagalimab treatment group will be set to Jeffreys prior Beta (0.5, 0.5) as non-informative. The probability that the posterior probability of rate difference  $> 0$  is larger than 90% is more than 90% if the endoscopic improvement rate difference is 25% between ravagalimab and historical placebo, given a sample size of 40 subjects for ravagalimab. If ravagalimab has the same endoscopic improvement rate of [REDACTED] as historical placebo, that probability is approximately 3.1%.

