11.0 Interim Analyses

After 30 ongoing subjects complete Week 8 assessments, an interim analysis will be performed in order to explore if proof of concept has already been demonstrated. This interim analysis will inform the planning of future Phase 2b and 3 studies. Enrollment into the induction period will continue until approximately 40 subjects have been enrolled. For this proof of concept study, no alpha adjustment will be conducted for this interim analysis.

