Table 7 shows the false positive rate and true positive rate for different assumed true placebo response rates and ravagalimab response rates given the historical placebo response rate is [REDACTED] respectively. Note the range of this placebo rate is determined by the 90% confidence interval of placebo rate based on meta-analysis. False positive rate is calculated as the probability that the posterior probability of rate difference > 0 is larger than 90% assuming there is no treatment difference between ravagalimab and placebo. True positive rate is calculated as the probability that the posterior probability of rate

difference > 0 is larger than 90% assuming there is a 25% treatment difference between ravagalimab and placebo.

[REDACTED] prior corresponds to borrowing [REDACTED] subjects with a historical placebo rate of [REDACTED] and [REDACTED] prior corresponds to borrowing [REDACTED] subjects with a historical placebo rate of [REDACTED]. Operating characteristics of using [REDACTED] prior are the similar as using [REDACTED] prior based on the calculation.

Based on [Table 7](#), within 90% confidence interval of placebo rate [REDACTED] 20 historical subjects or less could be borrowed while controlling false positive rates $< 10\%$ and not exceeding in study sample size.

D3. Comparison between ravagalimab and Placebo.

Posterior probability of rate difference [REDACTED] given the endoscopic improvement at Week 8 results, i.e., [REDACTED] will be calculated as follows. [REDACTED] are the response rates of ravagalimab and placebo, respectively.

Let n and N be the number of responders and number of subjects at Week 8. The conjugate priors used for [REDACTED] are [REDACTED] respectively. Therefore the posterior distributions for $\theta_{\text{ravagalimab}}$ and θ_{Placebo} will be [REDACTED] respectively. Note that in primary analysis, the

response rate is estimated using NRI-C which incorporates MI to handle missing data due to Covid-19; then the number of responders (n) is calculated based on the total number of subjects and estimated response rate, without rounding to an integer, to calculate the posterior probability.

Then the posterior probability is given by

$$\text{Posterior Probability} = \frac{\text{Beta}(n + \text{Beta prior}, m + \text{Gamma prior})}{\text{Beta}(n + \text{Beta prior}, m + \text{Gamma prior}) + \text{Beta}(n + \text{Beta prior}, m + \text{Gamma prior})}$$

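### Protocol 4.1 allows enrolment to end after the 30-subject interim, with no criterion, while Protocol 7.3 and SAP 11.0 continue to about 40; the stated decision probabilities and the SAP matching steps cover only the 40-subject trial

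*Protocol*

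**What the plan says.** **Enrolment after the interim.** Protocol 4.1 (Induction Period) places the interim when the 30th subject has completed Week 8 ("Week 8 assessments an interim analysis will occur"). It then gives two options: go on to about 40, or stop, because "enrollment may be terminated if the study objectives are determined to have been met". Protocol 7.3 (Interim Analysis) gives one: "Enrollment into the induction period will continue until approximately 40 subjects have been enrolled". SAP 11.0 repeats the 7.3 sentence. It also describes the look as being done "in order to explore if proof of concept has already been demonstrated", and states that "no alpha adjustment will be conducted for this interim analysis".

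**Decision probabilities.** Protocol 7.3 (Sample Size Estimation and Decision Probability) uses the event that the posterior probability of a positive rate difference exceeds 90%. It puts the chance of this at more than 90% for a 25-point effect, "given a sample size of 40 subjects for ravagalimab". For no effect it says "that probability is approximately 3.1"%. SAP Table 7 is titled for N = 40. From it, SAP Appendix D2 concludes that 20 or fewer historical subjects "could be borrowed while controlling false positive rates" below 10% across the 90% confidence interval of the placebo rate. That interval is redacted.

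**Matching.** SAP Appendix E4 times the propensity-score steps after 40 subjects are enrolled and before the primary database lock.

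**The concern.** All three enrolment statements are current text, and they direct different actions once the interim result is known. The study is open label and the interim examines efficacy, so the option in 4.1 could be used in practice.

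Three things follow if it is used. The quoted decision probabilities no longer describe the trial, because they contain no analysis at 30 and no stopping rule. The trigger for the matched-placebo analysis is never met. The final sample size comes to depend on the observed response, which pushes the estimate upwards in trials that stop for a good result, and this result is meant to inform Phase 2b and 3 planning.

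**Working it through.** **Inputs from the documents.** Ravagalimab prior Beta(0.5, 0.5); threshold 90%; N = 40; interim at 30; stated false-positive rate 3.1% (Protocol 7.3 and 4.1). Visible placebo counts are 4/65, 4/65 and 11/161, so 19/291, out of 325 in total (SAP Appendix D1). The other 325 − 291 = 34 subjects have a redacted count.

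**Assumption.** The placebo rate and prior are redacted. I take 6% worth 20 subjects, that is Beta(1.2, 18.8). Pooling gives 19/325 = 5.8% if the redacted study had no responders and 20/325 = 6.2% if it had one.

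**Step 1: reproduce the plan's figure.** With r responders of N, the treated posterior is Beta(0.5 + r, 0.5 + N − r). The smallest r for which P(treated rate > placebo rate) exceeds 0.90 is:
- N = 40: r = 6 (posterior 0.906; r = 5 gives 0.859)
- N = 30: r = 5 (posterior 0.922; r = 4 gives 0.869)

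P(X ≥ 6 | 40, 0.06) = 3.09%, which matches 3.1%. P(X ≥ 6 | 40, 0.31) = 99.4%, consistent with more than 90%.

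**Step 2: illustrate two looks.** Suppose success is declared at 30 by the same 90% rule, and otherwise judged at 40. The rate is P(X30 ≥ 5) + P(X30 < 5 and X40 ≥ 6).

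| True rate, no effect | One look at 40 | Two looks |
|---|---|---|
| 6% | 3.1% | 3.15% + 1.21% = 4.4% |
| 7% | 5.8% | 7.7% |
| 8% | 9.7% | 8.74% + 3.46% = 12.2% |

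The rate passes 10% at a true placebo rate of about 8.1% with one look and about 7.5% with two. For scale, the 90% Wald upper limit for the pooled 325 is 8.0% with no responders in the redacted study and 8.4% with one.

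**Step 3: count overrun.** Protocol 7.3 runs the primary analysis after all subjects complete induction, so subjects enrolled before a stop takes effect are counted. Keep the same prior, stop at 5/30 or more, and judge success on everyone enrolled:

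| Further subjects at the stop | True rate 6% | True rate 8% |
|---|---|---|
| 0 to 3 | 4.4% | 12.2% |
| 4 to 10 | 2.5% to 3.1% | 8.0% to 9.7% |

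The drop at four occurs because 5/33 still passes the threshold (0.904) and 5/34 does not (0.898). The switch point depends on the prior: one worth 40 subjects at 6% needs eight or more.

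**Step 4: vary the prior, with success declared at the interim.** At 6% worth 15 subjects, the two-look rate at a true 8% is 9.4%, passing 10% at about 8.2%. Worth 10 subjects, it is 4.7%. Neither reproduces 3.1% (both give 0.9% for one look at 6%), but SAP D2 allows any amount up to 20. Among combinations that do reproduce 3.1% (rates of 4.4%, 6.0%, 7.7% and 9.4%, worth 15 to 40 subjects), the two-look rate at the prior's own rate runs from 3.9% to 8.2%.

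**Step 5: size of the estimate's bias.** Among trials with at least 5/30 responders, the mean observed rate is 20.5% when the true rate is 15%, and 23.1% when it is 20%.

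**The case against.** The strongest reply is that the two-look model is not the documents' model. Nothing applies the 90% threshold at the interim. The trigger in 4.1 is that study objectives are met, and the objective in Protocol 3.1 is to explore efficacy, safety and tolerability. The summary of changes records that a proof-of-concept success criterion was removed to avoid a purely statistical test. The primary analysis uses all subjects, so overrun can remove the inflation altogether (Step 3). The lack of adjustment is stated openly in an exploratory Phase 2a study, and the figures are labelled for 40. Protocol 7.3 and SAP 2.4 also speak of up to approximately 40 subjects, which leaves some room to end below that number.

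Most of this stands, and it limits the point. A reader might infer that the trial breaches its bound of under 10%. The documents do not support that. The prior and the placebo interval are redacted, so 8% cannot be shown to lie inside the interval. The 3.1% belongs to the protocol's prior, which the SAP has since updated for the primary analysis. The excess also disappears under reasonable overrun or a lighter prior.

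The reply does not remove the conflict. The phrase about up to 40 concerns planned size, whereas the 7.3 and SAP 11.0 sentences say what happens after the interim. Declining to adjust alpha does not make a 40-subject figure describe a trial stopped earlier.

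**Conclusion.** The point holds as an inconsistency with consequences, not as a demonstrated loss of error control. One operative text permits a stop after 30 with no criterion and two say enrolment continues. The decision probabilities and the matching steps fit only the second course.

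Under 4.1 the false-positive rate is undefined as written. The illustrative figures, 4.4% against 3.1% at 6% and 12.2% against 9.7% at 8%, rest on three assumptions: a prior of 6% worth 20 subjects, the 90% rule used to declare success at the interim, and at most three further subjects if success is instead judged on all enrolled. At the central rate of 6% even the two-look figure is well under 10%. Correction is worthwhile because the texts must agree before the interim result is acted on.

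**What to change.** Preferred: delete the early-termination clause from Protocol 4.1, so that the interim informs planning only and enrolment goes to about 40, as in Protocol 7.3, SAP 11.0 and SAP Appendix E4. This changes one sentence and adds no one beyond the planned 40. It does give up the option of saving up to about 10 subjects, and a protocol amendment needs ethics committee review (Protocol 8.1).

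If the option is kept:
- change Protocol 7.3 and SAP 11.0 to allow it;
- pre-specify the interim criterion;
- state that the primary analysis uses all enrolled subjects, including overrun;
- restate the decision probabilities in Protocol 7.3, SAP 2.4 and SAP Table 7 for that rule;
- give SAP Appendix E4 a trigger that does not require 40 subjects.

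This costs some recalculation and possibly less favourable published figures.

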#### **Maintenance Period**

Subjects who enter the maintenance period will receive OL ravagalisimab 300 mg SC every other week (eow) from Week 12 through Week 102.

[figure not shown]
[figure not shown]
At Weeks 52 and 104 subjects will undergo endoscopy. Clinical response and remission, as well as other exploratory endpoints will be evaluated throughout the study at specified time points. Patients who complete the maintenance period will have a follow-up visit (or call if a visit is not possible) 84 days from the last dose of study drug to obtain information on any new or ongoing AEs.

The schematic of the study is shown in [Figure 1](#). Further details regarding study procedures are located in the Operations Manual.

See Section [5.1](#) for information regarding eligibility criteria.

All video endoscopies and mandatory biopsies for histologic assessment will be centrally reviewed.

**Figure 1. Induction and Maintenance Period Schematic**

**\*Bold= Study Visits +/- 7 days**

**\*\*84-day follow up visit/call from last study drug administration**

**Study Drug Administration Visits ONLY not listed in the schematic above and will occur at:**

**Week 14, 18, 22, 24, 26, 30, 32, 34, 38, 40, 42, 46, 48, 50, 54, 56, 58, 60, 62, 66, 68, 70, 72, 74, 78, 80, 82, 84, 86, 90, 92, 94, 96, 98, 100, 102**

**BL = Baseline; EOW = every other week; IV = intravenous; SC = subcutaneous**

**Note: Prior to protocol version 4.0 the study had a double-blind (DB) placebo-controlled induction period.**

## 4.2 Discussion of Study Design

---

### Choice of Control Group

The efficacy of ravagalimab will be evaluated through comparison with historical control. The control group for this study is placebo data derived from meta-analysis of recent clinical studies that used central review of endoscopies and that are aligned in terms of endpoint definition and time point of analysis. The objective nature of the centrally read endpoint, as well as the low placebo rate of endoscopic improvement, makes the use of historical placebo control a feasible method to assess the effect of ravagalimab. Subjects will therefore not be enrolled into a concurrent control group within the study.

Prior to Version 4.0, a concurrent placebo control arm was used in this study.

### Appropriateness of Measurements

Standard data collection, clinical, statistical, endoscopy-related and laboratory procedures will be utilized in this study. All efficacy measurements in this study are standard or are derived from commonly used efficacy measurements for assessing disease activity in clinical studies of subjects with UC. All clinical and laboratory procedures in this study are standard and generally accepted. Central review of endoscopy will increase study rigor and ensure enrollment of subjects with moderately to severely active UC.

### Suitability of Subject Population

The specific population chosen was based on the unmet medical need of those subjects who have failed prior therapy as defined in Section 5.1.

### Selection of Doses in the Study

The dose selection in this study is based on analysis of PK, pharmacodynamics, and safety data from Phase 1 studies in healthy volunteers as well as safety data from pre-clinical animal studies. The Phase 1 ravagalimab single and multiple ascending dose studies, Study M15-726 and Study M15-730, evaluated ravagalimab single doses of 10 - 300 mg SC and 100 - 600 mg IV, and multiple doses of 50 and 150 mg SC weekly for 3 weeks following IV loading doses of 50 mg and 300 mg, respectively. Partial peripheral blood B cell CD40 RO was achieved with SC doses of 10 and 30 mg; whereas full peripheral blood B cell CD40 RO (i.e., > 90%) was achieved with IV or SC doses  $\geq$  100 mg. In Study M15-730, full peripheral blood B cell RO was achieved with weekly SC doses of 50 and 150 mg and was maintained for at least 14 days after the last ravagalimab dose.

In Study M16-641 the impact of ravagalimab on T helper dependent B cell responses following keyhole limpet hemocyanin (KLH) administration was evaluated. Preliminary results from the study showed that a single 300 mg SC dose of ravagalimab achieved near full suppression of IgM and IgG response to KLH antigen. On the other hand, a single 100 mg SC dose and multiple 100 mg SC doses given once every two weeks (total of three doses) resulted in minimal to no suppression of immune response to KLH, despite prolonged maximal peripheral blood B cell CD40 RO.

Given the results from the KLH immunization study and the uncertainty in correlation between peripheral blood B cell CD40 RO and efficacy in UC patients and the potential for a tissue sink in UC

patients, for this proof-of-concept (POC) study, a 600 mg IV loading dose followed by 300 mg eow SC dose was selected for induction to enable rapid achievement of serum steady state ravagalimab concentrations as well as presumably high levels of tissue RO. Such dosing is predicted to provide at least a 20-fold safety margin relative to no-observed-adverse-effect-level (NOAEL) exposures observed at a dose of 50 mg/kg in the 13-week GLP-compliant toxicology study in cynomolgus monkeys. Given the high inflammatory burden for UC patients, a 300 mg eow SC maintenance dose was selected for subjects who demonstrate clinical response after induction. Furthermore, 300 mg eow SC dosing with ravagalimab is predicted to result in serum ravagalimab exposures that are approximately 4-fold lower than the NOAEL exposures observed at a dose of 5 mg/kg in 26-week toxicology studies in cynomolgus monkeys.

## 5 STUDY ACTIVITIES

### 5.1 Eligibility Criteria

---

Subjects must meet all of the following criteria in order to be included in the study. Anything other than a positive response to the questions below will result in exclusion from study participation.

#### Consent

- 1. Subjects must understand and personally, voluntarily **sign and date an informed consent**, approved by an independent ethics committee (IEC)/institutional review board (IRB), prior to the initiation of any screening or study-specific procedures.

